3.2.2 Sampling

HIV-1-positive patients on a stable antiretroviral regimen for whom DTG/RPV is indicated according to the local SmPC may be selected for inclusion. The decision for prescription of the treatment regimen must be completely independent from study inclusion. However, patients eligible for inclusion, should be included with start of the new therapy regimen. Eligible patients must meet all inclusion and none of the exclusion criteria and must be thoroughly informed about all aspects of the study. The written informed consent must be obtained from the patient before any patient data is documented into the eCRF.

Investigators may enroll eligible subjects according to their availability and accessibility. The sample is deliberately non-stratified to reduce limitations on recruitment. This non-probabilistic convenience sampling may not ensure for the sample group to be a true representative of the population without sampling error.

Thus, this approach may result in some characteristics not being represented within the sample and limited diversity in terms of demographics and introduction of confounding factors, which may be considered in subgroup analysis

But as there are few further restrictions introduced by inclusion / exclusion criteria other than what is permitted under the local label, this study may provide evidence for a patient population that is broader than that of controlled clinical trials.

3.3 Data Source / Data Collection

3.3.1 Data documented by study sites

Data will be collected from routine clinical care. Follow-up visits will not exceed those recommended by local guidelines, which suggest routine follow ups every 2-4 months. The frequency of follow-up visits is not defined by the study protocol due to the nature of a non-interventional study and is completely at the discretion of the treating physician. Every regular follow-up should be documented as a study visit. Additional patient contacts that merely involve blood sampling (e.g. viral load re-tests) without any further examination, will not need to be documented as study visits. However, the results of the viral load assessments should be documented. Data may be obtained from clinical records and findings, observations or other sources (e.g. hospital records, clinical and office charts, electronic patient records, laboratory notes).

3.3.2 Patient reported data sources (non-mandatory)

At baseline, first follow up and additionally at 12, 24 and 36 months, patients will be asked to complete the HIV Symptom Distress Module [11] (also called the HIV Symptom Index or Symptoms Impact Questionnaire) and the HIV treatment satisfaction questionnaire (TSQ) [12] on a voluntary basis.

The Symptom Distress Module is a 20-item self-reported measure that addresses the presence and perceived distress linked to symptoms commonly associated with HIV or its treatment [11]

The HIV TSQ is a 10-item-self-reported scale that measures overall satisfaction with treatment and by specific domains e.g., convenience, flexibility [12].

At baseline and at each follow-up visit, patients will also be asked to give an estimation of their level of adherence to their ART.

3.3.3 Data collection

All country-specific, national and international legal requirements for data handling and data archiving will be met. Data will be collected using CVEDC, which is an electronic data capture (EDC) system compliant with Good Clinical Practice (GCP) and 21 code of federal regulations (CFR) part 11. CVEDC is technically based on an XML interexchange model called ODM (operational data model) which is implemented and validated by the clinical data interchange standards consortium (CDISC) data standards. All data safety regulations will be met by the system.

Medical data in this study will be recorded directly in the eCRF system without the use of study specific paper documents. The eCRF system will be available to all participating sites over the entire duration of the study. When the system is no longer available (at database closure), all participating sites will be provided with a DVD with PDFs of all site-specific data and metadata (e.g. audit trail, data queries).

3.4 Endpoints

All primary and secondary endpoints described under 3.4.1 and 3.4.2 are planned to be analyzed in respect of the total study population and in following subgroups:

- Gender
- Age
- Baseline CD4 cell count
- Baseline treatment status
- Prior therapy
- CDC status
- Baseline comorbidities

3.4.1 Primary Endpoint

Proportion of patients with sustained virologic suppression, defined as VL < 50 c/ml or if between 50-200 c/ml with a subsequent next available measurement* (within 120 days) < 50 c/ml at year 1, 2, and 3.

3.4.2 Secondary Endpoints [analyzed at year 1, 2, 3 unless otherwise stated]

- Proportion of patients with low level viremia, defined as a VL measurement >50 - <200 c/ml
- Proportion of patients with VL >50 c/ml with emergent resistance mutations (if available)
- Proportion of patients with virologic rebound, defined as two consecutive VL measurements \geq 200 c/ml
- Proportion of patients with two consecutive measurements of \geq 200 c/ml, or treatment switch due to VF or due to intolerance as determined at the discretion of the physician
- Proportion of patients VL <50 c/ml
- Number of monitoring measures [normalized to patient years]
- Number and frequency of serious adverse events (SAEs) [normalized to patient years]
- Number and frequency of adverse drug reactions (ADRs) [normalized to patient years]
- Adherence to therapy [refers to missed monthly doses]
- Change in lipid laboratory values

- Change in treatment satisfaction [HIV Treatment Satisfaction questionnaire]
- Change in symptom distress [HIV Symptom Distress Module questionnaire]
- Reason for switch to Juluca

[* Any subsequent measurement will be accepted as a consecutive measurement as long as measured no later than 120 days after the initial measurement. If no subsequent VL measurement is performed within 120 days this is scored as a confirmed VL.]

3.5 Sample Size / Power Calculations

Recruitment target is a total of N=250 patients. Based on both SWORD-1 & -2 protocol assumptions (87%) and actual efficacy rate (95%), we assumed an efficacy rate of 90%.

We further assumed a max. drop-out rate of 30% over the study period of 3 years, based on the two non-interventional studies TRIUMPH and DOL-ART.

With an anticipated antiviral efficacy of 90% and a level of confidence of 95% with a target width of 0,1 (10%), a total number of N=158 patients are needed after the observational period of 3 years. Calculating with a max. 30% drop-out rate, N=226 subjects have to be included into the study. Therefore, our goal is to recruit N=250 subjects.

Patient numbers were calculated using the PASS software.

3.6 Hypotheses

The study is not hypothesis testing, but rather of descriptive nature, with the aim of generating real-world evidence for the use of DTG/RPV in routine clinical care in Germany to supplement data obtained from controlled clinical trials. Thus, statistical analysis will be of descriptive nature only.

4 DATA ANALYSIS CONSIDERATIONS

Standard descriptive methods will be used to analyze all data. Continuous variables will be summarized using the number of observations, mean, median, standard deviation and interquartile range. Categorical variables will be summarized using the number of observations and percentages. To investigate the consistency of observations, analyses will be carried out for total study population as well as for subgroups; e.g.:

- Gender
- Age
- Baseline CD4 cell count
- Treatment status
- Prior therapy
- CDC status
- Baseline comorbidities

Questionnaires will be analyzed according to the validated scoring instructions of the respective questionnaires. When evaluating change from baseline only complete pairs will be analyzed.

Due to the descriptive nature of the analyses, missing data will not be substituted or recoded.

Detailed methodology for summary and statistical analysis of data collected in this study as well as data sets will be specified in a Statistical Analysis Plan (SAP) prior to database lock.

5 LIMITATIONS

This is a non-interventional single-arm study aimed at gathering real-word data for the use of Juluca in routine clinical care in Germany. And as such there are a number of limitations, such as data source and geographic limitations. The sample is deliberately non-stratified to reduce limitations on recruitment. And with convenience sampling, the population may also be subject to selection bias.

Thus, this approach may result in some characteristics under- or overrepresented within the sample and limited diversity in terms of demographics and introduction of confounding factors, which may be considered in subgroup analysis.

However, real world data may provide valuable evidence for a patient population that is broader than that of controlled clinical trials, thus enhancing the generalizability and transferability of findings despite large random variations due to a heterogenic patient population.

6 STUDY CONDUCT, MANAGEMENT & ETHICS

6.1 Ethics Committee/IRB Approval

Prior to the start of this study, the protocol, the proposed informed consent form and other information for subjects will be reviewed by a properly constituted Ethics Committee. A signed and dated statement that the protocol and informed consent have been approved by the Ethics committee must be obtained before study initiation. Any amendments to the protocol, other than administrative ones (for which the Ethics Committee will merely be informed), must be reviewed and approved by the Ethics Committee. Once a favorable opinion from the competent Ethics Committee has been granted, the study will be reported to the Federal Institute for Drugs and Medical Devices (BfArM). Furthermore, in accordance with the applicable regulations, the study and the participating investigators will be reported to the National Association of Statutory Health Insurance Funds (GKV-SV) and any and all payments made by VH will be made public.

6.2 Informed Consent

6.2.1 Written informed consent

The investigator will ensure that each study patient, or his legally acceptable representative, is fully informed about the nature and objectives of the study. The investigator, or a person designated by the investigator, will obtain written informed consent from each patient or the patient's legally acceptable representative before any study-specific activity is performed. The investigator will retain the original of each patient's signed consent form.

6.2.2 Withdrawal of consent

Patients may withdraw from the study at any time at their own request without giving reason for doing so without penalty of prejudice. There will be no consequences for subsequent medical treatment. In case a patient wishes to withdraw, the investigator may attempt to inquire about the reason for withdrawal and follow-up on unresolved adverse events. The patient may also withdraw permission for use of any data collected up until this point.

6.2.3 Withdrawal from the study by investigator or sponsor

Furthermore, patients may be withdrawn at any time at the discretion of the investigator or sponsor for safety, behavioral, or administrative reasons. The investigator should withdraw any patient who is known to have had a period of non-adherence >28 days.

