Regardless of the current treatment status of a patient, antiretroviral therapy must be taken lifelong to ensure suppression of viral replication, which is the overarching treatment goal and reduces the risk of HIV-associated complications, such as immunosuppression and the occurrence of opportunistic infections, as well as a chronic inflammation, which can result in a higher risk for cardiovascular events. Although antiviral therapies have been improved over the last decades in terms of efficacy and tolerability, most therapies require 3 or more drugs to achieve the overarching therapy goal of viral suppression. This is accompanied with the risk of drug-drug interactions, especially in the case when pharmacologic boosters are required to improve PK-profiles of distinct substances, such as protease-inhibitors and the integrase-inhibitor Elvitegravir [5]. Providing therapies with only two drugs, as in Juluca (DTG / RPV), addresses this obstacle in therapy, with a complete antiretroviral regimen with just 2 active substances. This might be beneficial in terms of pharmacology, especially taking into account that over 50% of all patients living with HIV in Germany are 45 years of age and older. Recent publications have shown, that about 20% of the general population, irrespective of their HIV status, have an intake of at least 2 non-ART drugs in that age category of 50 years or older [9]. Furthermore, it might be beneficial in terms of reducing the overall substance burden during a patients' life, when considered, that patients who have been infected and started their therapy between 2008 and 2010, have a life-expectancy of 78 years, meaning almost six decades of antiviral therapy [10].

Non-interventional studies (NIS) provide insights into the medication use in routine clinical care and generate real-world evidence for the used ART in terms of efficacy and tolerability, which can supplement data from randomized clinical trials.

ViiV Healthcare (VH) Germany is currently sponsoring two NIS, DOL-ART and TRIUMPH, observing patients taking either DTG or Triumeq in routine clinical care. Data generated in both studies are published regularly twice a year on national and international conferences to inform HCPs about the real-world profile of DTG when it is used in routine clinical care in Germany.

Likewise, a prospective multicenter NIS for Juluca will assess the drug profile of the first 2DR in a routine clinical setting in Germany.

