2.2 Secondary

- Gain an understanding of the major relevant patient populations for Juluca in Germany, in terms of patient characteristics and history
- Describe real-life efficacy profile of Juluca
- Describe real-life tolerability profile of Juluca as measured by discontinuation rates due to adverse drug reactions (ADRs) and overall number of serious adverse events (SAE)
- Analyze the development of viral resistance by evaluating available resistance data in case of virologic failure
- Describe impact on lipid metabolism
- Evaluate medical need for a substance and/or class sparing treatment regimen by assessing the reason for switching to Juluca
- Describe patients' treatment satisfaction and symptom distress based on validated questionnaires
- Evaluate number of monitoring measures and referrals to other specialists

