## 10 Statistical Methods

### 10.1 Definition of analysis time window

### 10.2 Year 1, 2, and 3 follow-up windows

**Year 1 follow-up window** is defined as 9 to 15 months [275 days; 457 days] after the therapy start. This window applies to all variables incl. patient reported outcomes.

Rule for two or more assessments in the time window:

The closest available assessment to year 1 (365 days) after therapy start while the participant is on treatment and continued on study within the time window.

**Year 2 follow-up window** is defined as 21 to 27 months [640 days; 822 days] after the therapy start. This window applies to all variables incl. patient reported outcomes.

Rule for two or more assessments in the time window:

The closest available assessment to year 2 (730 days) after therapy start while the participant is on treatment and continued on study within the time window.

**Year 3 follow-up window** is defined as 33 to 39 months [1005 days; 1185 days] after the therapy start. This window applies to all variables incl. patient reported outcomes.

Rule for two or more assessments in the time window:

The closest available assessment to year 3 (1095 days) after therapy start while the participant is on treatment and continued on study within the time window.

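### Protocol 6.2.3 has participants withdrawn after a known non-adherence gap of more than 28 days, and the SAP does not say how they count in the suppression and adherence results

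*Protocol*

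**What the plan says.** Protocol 6.2.3 first allows withdrawal at the discretion of the investigator or sponsor for safety, behavioural or administrative reasons. It then adds a directive sentence: "The investigator should withdraw any patient who is known to have had a period of non-adherence >28 days". It gives no reason, and neither amendment changes it.

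The aims point towards routine practice. Protocol 3.6 describes "generating real-world evidence for the use of DTG/RPV in routine clinical care in Germany", and a secondary objective in 2.2 is "Describe real-life efficacy profile of Juluca". The primary endpoint in 3.4.1 begins "Proportion of patients with sustained virologic suppression, defined as VL < 50 c/ml"; the SAP makes year 3 primary (11.3.1) and moves years 1 and 2 to the secondary endpoints (11.3.2). Protocol 3.4.2 lists "Adherence to therapy [refers to missed monthly doses]" as a secondary endpoint. Under 3.3.2, at baseline and each follow-up visit, "patients will also be asked to give an estimation of their level of adherence to their ART".

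The SAP does not refer to the 28-day rule. Where a year-3 window holds two or more assessments, SAP 10.2 takes the "closest available assessment to year 3 (1095 days) after therapy start while the participant is on treatment and continued on study". SAP 10.3 bases proportions on non-missing data and imputes nothing except HIVTSQs scores. SAP 8.2 removes two groups from the effectiveness set: those lost to follow-up, and those still taking the drug who have no viral load in the window. SAP 11.3.1 lists only loss to follow-up as a reason for exclusion from the primary analysis.

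**The concern.** A long treatment gap is both a value of one endpoint (adherence) and a plausible cause of failure on another (suppression). The protocol's Introduction makes the link itself: "antiretroviral therapy must be taken lifelong to ensure suppression of viral replication". Ending participation because of a gap therefore conditions the later results on something that happened after enrolment and is related to the outcome. The adherence question asked at visits can also be what brings the gap to light, so the adherence results can lose their worst values through their own measurement.

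At stake is whom the year-3 figure describes. If the withdrawn participants drop out of it, it describes those not known to have had a long gap, but it would be read as real-life suppression. The limitations in Protocol section 5 cover convenience sampling, data source and geography. They do not mention selection after enrolment.

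**Working it through.** **1. The plan's own figure.** Protocol 3.5 assumes 90% efficacy and a 95% interval of full width 0.10. The exact (Clopper-Pearson) interval has width 0.1001 at n = 157 and 0.0997 at n = 158, so 158 reproduces. With 30% drop-out, 158 / 0.70 = 225.7, which rounds up to 226 and also reproduces. Precision is not in question. The planned half-width of 5 points is a yardstick for the bias, which a larger sample would not remove.

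**2. What is lost and what is kept.** Only windows after withdrawal are lost: a participant withdrawn in month 30 can still contribute years 1 and 2. The SAP flow chart (7.4) schedules adherence, laboratory values, resistance testing, both questionnaires, the date and reason, and subsequent therapy at discontinuation. Rebound and the rebound-or-switch composite (11.3.2) run from baseline to year 3, so viral loads before withdrawal can count. SAP 11.3.5 tabulates discontinuation reasons but lists the last HIV-RNA only for virologic discontinuations, so a non-adherence withdrawal falls outside that listing.

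**3. Two readings of the year-3 denominator.**
- Reading A: with no on-study value in the window, the participant leaves through the non-missing denominator (SAP 10.2 and 10.3).
- Reading B: SAP 8.2 and 11.3.1 do not name investigator withdrawal as an exclusion, so the participant stays in the effectiveness set and is counted as not suppressed.

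**4. Size under each reading.** Let f be the share of otherwise evaluable participants withdrawn under the rule, and s the proportion of them who would be suppressed at year 3 if followed. The rest are taken at 90%, the planning value in Protocol 3.5. The values of f and s are assumptions.
- All participants: 0.90(1 − f) + s·f. With s = 0.50 this is 0.90 − 0.40f.
- Reading A reports 0.90. Overstatement = f(0.90 − s) = 0.40f.
- Reading B reports 0.90(1 − f). Understatement = s·f = 0.50f.

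| f | All participants | Reading A | Error (points) | Reading B | Error (points) |
|---|---|---|---|---|---|
| 2% | 89.2% | 90.0% | +0.8 | 88.2% | −1.0 |
| 5% | 88.0% | 90.0% | +2.0 | 85.5% | −2.5 |
| 10% | 86.0% | 90.0% | +4.0 | 81.0% | −5.0 |

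**5. Sensitivity.** With f from 1% to 10% and s from 30% to 90%, the overstatement under Reading A runs from 0 (s = 90%) to 0.10 × 0.60 = 6.0 points. It reaches the 5-point half-width at f = 0.05 / 0.40 = 12.5% for s = 50%, or 0.05 / 0.60 = 8.3% for s = 30%.

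**The case against.** The strongest defence is that the objective concerns patients using Juluca and its antiretroviral efficacy, so an on-treatment estimate that stops after a long known gap is a legitimate choice. The rule also says *should* and reaches only known gaps, so removal will be incomplete. Discontinuations and their reasons are reported, so the loss is visible. All of this stands as far as it goes. It does not meet the point that neither document states such an estimand, that adherence is itself an endpoint, and that tabulating reasons does not show how the year-3 proportion would change.

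Three stronger readings are tempting, and the documents do not support them.
- *Suppression will be overstated.* That follows under Reading A only. The SAP does not settle between the two readings, and under Reading B the error goes the other way.
- *All year 1 to 3 data on these participants are lost.* Only windows after withdrawal are affected. The on-study wording in SAP 10.2 also appears under the rule for choosing among several assessments, not as a general eligibility rule.
- *The study cannot answer its primary objective.* This is not shown. At s = 50%, the overstatement stays below the 5-point half-width across the 2% to 10% range, and the withdrawal rate is unknown.

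**Conclusion.** The concern holds as a selection problem combined with a gap in the SAP. The rule removes participants on a post-baseline variable related to the primary outcome, and no provision keeps them under observation afterwards. The adherence results after withdrawal are cut off at their worst end, whichever denominator is used for suppression.

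For the primary proportion, neither the direction nor the size of the error can be fixed from the documents. That those withdrawn would do worse than the rest is a reasonable inference with only qualitative support in the protocol. If they are excluded, overstatement is the likely result. If they are counted as not suppressed, the figure is too low whenever any of them would have been suppressed. The year-3 estimate thus describes a narrower population than its label suggests, or depends on an unstated classification.

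**What to change.** **SAP (8.2, 11.3.1, 11.3.5).**
- Identify participants withdrawn under the 28-day sentence from the recorded discontinuation reason, including the free text under the category for other reasons. The documents do not show non-adherence as a coded reason, so the free text matters.
- Report their number and last on-study HIV-RNA.
- State how they are classified at years 1, 2 and 3.
- Report the year-3 proportion with them excluded, and again with them in the denominator as not sustained. Label the second a conservative lower bound, because some of them may have been suppressed. A third version by last HIV-RNA is optional.
- Use HIV-RNA dated after withdrawal only where consent permits.

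**SAP 11.3.4.** Show these participants as a separate category in the adherence table.

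**Protocol 6.2.3.** If follow-up is still open, reconcile the sentence with the real-life objective so that such participants can stay under routine documentation. This concerns study participation only, not treatment. Amendment 1 shows sites enrolling by December 2018 for about three years of follow-up, and the SAP dates from 2023, so the SAP route is probably the practical one.

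**Cost.** A few lines of SAP text, a review of discontinuation reasons and one additional table. The reported proportion may become less favourable or be given as a wider range.
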